2.5. Previous clinical experience with ChAdOx1-MVA 5T4 vaccine

VANCE01 was the first phase I clinical trial to assess the safety and immunogenicity of ChAdOx1-MVA 5T4 vaccine. VANCE01 began in Oxford in June 2015 (NCT02390063) and completed in May 2018. It compares ChAd-MVA vaccination to MVA alone, with and without low dose cyclophosphamide in low- and intermediate-risk localised prostate cancer.

An initial clinical assessment of the vaccine has shown it to be both safe and immunogenic for cellular and antibody responses to the 5T4 protein. The study design and further details of this

trial are given below.

Randomised, open label trial

To date, 40 patients have been enrolled and 39 of these have completed the vaccination course comprising either a standard immunisation protocol of 3 immunisations given at 4 week intervals or an accelerated protocol of 2 immunisations given at a 1 week interval.

The majority of adverse events were mild in nature and the interim clinical safety review was satisfactory. Both ChAdOx1.5T4 and MVA.5T4 vaccines have been well tolerated in both the standard prime-boost and the accelerated prime-boost vaccination regimes. Systemic reactogenicity appears most pronounced following the accelerated vaccination regime after the MVA.5T4 boost, but all symptomatic manifestations have been self-limiting and quickly resolving. Derangements in clinical haematology and biochemistry have all been mild and transient in nature. No additional safety findings are apparent following vaccination in combination with low dose cyclophosphamide. There has been one serious adverse event (SAE) which was deemed unlikely to be related to the investigational medicinal products employed in this study.

Overall, ChAdOx1-MVA 5T4 vaccine was safe and well tolerated. An initial assessment of immunogenicity is very encouraging given that 5T4 is a self-antigen against which an immunological tolerance is likely to exist. More than 60% of the patients in VANCE01 have mounted cellular 5T4 specific responses that are readily detectable *ex vivo*. A summary of the cellular immune responses observed to date are shown in Figure 7. Of note, the elicited immune responses were comparable between the standard 4 week vaccination regime and the accelerated 1 week immunisation schedule, but CTX pre-conditioning has not improved vaccine immunogenicity. Therefore, in ADVANCE study CTX will not be administered and a 2 week interval between ChAdOx1.5T4 prime and MVA.5T4 boost will be deployed in order to minimise surgery.

delay for intermediate-risk prostate cancer patients and at the same time to allow sufficient time for the immune cells to mediate their effect on the target organ.

[figure not shown]

Figure 7. Summary of 5T4-specific cellular immune responses. Each dot represents the magnitude of the largest response at any post vaccination time point for each responding subject.

2.6. Previous clinical experience with PD-1 blockade in prostate cancer

PD-1 blockade as a monotherapy

Results to date examining PD-1 blockade alone have suggested little role for these treatments as monotherapy for patients with prostate cancer. Clinical efficacy of PD-1 therapy (nivolumab) in mCRPC has been assessed in two independent phase 1 trials. Despite evidence showing that CD8 T cells infiltrating prostate tumours express PD-1, no objective responses to single-agent PD-1 blockade were reported in the 25 patients with prostate cancer who were treated in both of these trials^{8,9}.

More recently, however, an unexpected clinical activity of PD-1 blockade was seen in mCRPC patients progressing on ENZ³³. Patients with evidence of progression on enzalutamide were treated with anti-PD-1 mAb (pembrolizumab) 200 mg IV every 3 weeks for 4 doses. Anti-PD-1 mAb was added to standard dose of enzalutamide. Three of the first ten patients enrolled in this ongoing phase II trial experienced rapid PSA reductions to ≤ 0.2 ng/ml. Two of these three patients had measurable disease upon study entry and both of these patients achieved a partial response. A phase II trial is currently underway that more thoroughly examines the antitumor efficacy of PD-1 blockade in patients with mCRPC (NCT02312557).

As mentioned earlier, a large multi-centre international trial, KEYNOTE-199, evaluating pembrolizumab as a monotherapy in 370 patients with metastatic castration resistant prostate cancer is currently ongoing (NCT02787005). Preliminary results from 258 patients already

recruited to the trial were reported by De Bono and colleagues at the ASCO annual meeting in June 2018 and showed that pembrolizumab had antitumour activity in 11% of both PD-L1 positive and PD-L1 negative patients with mCRPC.

PD-1 blockade in combination with vaccines

It remains to be determined whether PD-1 blockade will be more effective in patients with prostate cancer when used in combination with other treatments. To address this question, several trials are currently underway to the assess clinical activity of PD-1 in combination with vaccines.

In one trial, mCRPC patients are treated with anti-PD-1 (pembrolizumab) in combination with plasmid DNA vaccine (pTVG-HP) encoding prostatic acid phosphatase (PAP). This pilot phase I study will recruit 32 patients who will be randomized to two arms to receive 6 doses of the vaccine and four infusions of anti-PD-1 either concurrently or sequentially (NCT02499835).

In the second trial, anti-PD-1 mAb (nivolumab) is administered in combination with PROSTVAC vaccine. Three doses of nivolumab (240mg per dose) are administered at the same time as the booster vaccinations given 3 weeks apart. This study is recruiting cancer patients who are surgical candidates for radical prostatectomy and the experimental treatment is given as a neoadjuvant prior to surgery (NCT02933255).

Data collection for both studies is ongoing and the final results are not expected within the next couple of years.

3. OBJECTIVES

Primary objectives

Low- or intermediate-risk PCa patients:

- To assess safety of the viral vectored ChAd-MVA 5T4 vaccine when administered in combination with anti-PD-1 mAb
- To determine whether ChAd-MVA 5T4 vaccine in combination with anti-PD-1 will impact on the level of PSA in the blood

Metastatic PCa patients:

- To assess safety of the viral vectored ChAd-MVA 5T4 vaccine when administered in combination with anti-PD-1 mAb
- To assess efficacy of the viral vectored ChAd-MVA 5T4 vaccine when administered in combination with anti-PD-1 mAb as measured by composite response rate defined as one of the following:

- reduction of circulating tumour DNA of $\geq 50\%$
- serum PSA decrease of $\geq 50\%$

Secondary objectives

Low- or intermediate-risk PCa patients:

- To assess the magnitude of immune responses in the periphery generated by ChAd-MVA 5T4 vaccine in combination with anti-PD-1 mAb
- To assess immune cell subsets in the prostate secondary to treatment

Metastatic PCa patients:

- To assess the magnitude of immune responses in the periphery generated by ChAd-MVA 5T4 vaccine in combination with anti-PD-1 mAbTo evaluate radiographic progression-free survival at 6 months and one year post enrollment
- To evaluate overall survival at 6 months and one year post enrollment

Exploratory objectives

- To investigate whether ChAd-MVA 5T4 vaccine in combination with checkpoint blockers will lead to up-regulation of PD-L1 expression in the primary tumour or metastatic lesion
- To determine whether ChAd-MVA 5T4 vaccine in combination with PD-1 mAb will impact on the level of PSA-related kallikreins in the blood
- To assess biochemical (PSA) response rates according to PCWG2 criteria
- To assess whether ChAd-MVA 5T4 vaccine administered in combination with anti-PD-1 mAb will lead to reduction of circulating tumour cells
- To evaluate phenotypic and functional profile of immune cells in the blood secondary to treatment
- To evaluate immunologic antigen spreading to other prostate-associated antigens secondary to treatment

4. STUDY DESIGN

4.1. Study overview

This is a phase I/II open label non-randomised study to determine the safety and immunogenicity of the viral vectored ChAd-MVA.5T4 vaccines in combination with anti-PD-1 checkpoint blockade in low- or intermediate-risk localised or locally advanced prostate cancer and in metastatic prostate cancer.

This is an adaptive design study. A number of modifications to the protocol may be implemented on review of interim safety and efficacy data, following evaluation by the trial's independent data

and safety monitoring committee. One of the possible modifications may include sample size re-calculation. Subjects with low- or intermediate-risk disease and metastatic prostate cancer enrolled to the study will be evaluated for markers of treatment efficacy using the primary study endpoints (i.e. circulating tumour DNA and PSA kinetics) and vaccine-specific and non-specific immune responses. In the event that interim analysis indicates an early efficacy signal among a particular population of study participants, a sample size re-calculation may be undertaken and recruitment targets adjusted to provide enhanced power on efficacy analyses. Sample size re-calculation and group size adjustments will be made with the oversight of the study independent data and safety monitoring committee and subject to satisfactory interim safety profile of the groups involved. Additionally, if the patients demonstrate a clinical response to the study treatment, the number of vaccinations and/or nivolumab infusions can be increased.

Any changes to the study design will constitute a substantial amendment and, therefore, will be reviewed and approved by the Sponsor, REC/HRA, and MHRA (if appropriate) prior to implementation.

4.2. Investigational products

The investigational products to be used in this study are:

- ChAdOx1.5T4
- MVA.5T4
- Nivolumab (anti-PD-1 monoclonal antibody)

4.2.1 Vaccine formulation, storage and accountability

ChAdOx1.5T4

ChAdOx1.5T4 vaccine is an unlicensed medicinal product manufactured by the University of Oxford Clinical Biomanufacturing Facility (CBF), Churchill Hospital, Oxford. It is formulated in formulation buffer at a nominal concentration of 1.1×10^{11} vp/mL. The formulation buffer consists of 10mM Histidine, 7.5% sucrose, 35mM NaCl, 1mM MgCl₂, 0.1% PS80, 0.1mM EDTA, 0.5% EtOH, pH 6.6. The fill volume is 0.5-1.0 mL. The dose of ChAdOx1.5T4 to be used in this study is 2.5×10^{10} vp. It is manufactured, labelled and released under Good Manufacturing Practice conditions to the clinical sites by the CBF. All movements of the study vaccine between the CBF and the clinical sites will be documented. The vaccine is supplied as liquid in glass vials and is stored at -80C in a locked, alarmed, temperature monitored freezer prior to release to the clinical sites. Following shipment to sites, the vaccine is stored as above, however, short-term storage for up to 3 months at 2-8C is acceptable if required, based on the manufacturer's stability data to date.

MVA.5T4

MVA.5T4 vaccine is an unlicensed medicinal product that has not been administered to humans before. VANCE01 trial has made use of the biologically equivalent MVA.5T4 vaccine supplied by Oxford BioMedica (manufactured by Baxter), trade name TroVax®. The new batch of MVA.5T4

vaccine expresses the 5T4 antigen under control of the different poxvirus promoter. It has been manufactured under Good Manufacturing Practice conditions by IDT Biologika GmbH, Germany. MVA.5T4 is supplied as a frozen liquid formulation in 10mM Tris buffer 140 mM NaCl, pH 7.7 in 2.0 mL clear glass vials. The formulation titre is 2×10^9 pfu/ml, the final drug product titre is 1×10^9 pfu/ml. The fill volume is 0.55 mL. Further details relating to batch manufacture can be found in the MVA.5T4 IMPD.

To ensure consistency with the VANCE01 clinical trial and all previous University of Oxford trials using MVA vectored vaccines, the dose to be used in this study will be 2×10^8 pfu. The vaccine will be labelled and released under Good Manufacturing Practice conditions to the clinical sites by the CBF. All movements of the study vaccine between the CBF and the clinical sites will be documented. At CBF it is stored at -80C in a locked, alarmed, temperature monitored freezer prior to release to the clinical sites. Following shipment to sites, the vaccine is stored as above.

Minimising environmental contamination with Genetically Modified Organisms (GMO)

In order to minimise dissemination of the recombinant virus into the environment, the inoculation site will be covered with a dressing after immunisation. This should absorb any virus that may leak out through the needle track. The dressing will be removed from the injection site after 60 minutes (\pm 15 minutes) and will be disposed of as GMO waste by autoclaving as well as unused/expired vaccine vials, in accordance with the relevant Standard Operating Procedure (SOP) and current standard UK practice.

Checkpoint inhibitor formulation, storage and accountability

4.2.2 Anti-Programmed Death Receptor-1 (PD-1) antibody - nivolumab (Opdivo®)

Nivolumab (Opdivo®) is a human immunoglobulin G4 (IgG4) monoclonal antibody directed against programmed death-1 (PD-1) receptor. It is a licenced pharmaceutical product manufactured and marketed by Bristol Myers Squibb Pharmaceutical Limited. It holds a UK licence for the treatment of unresectable or metastatic advanced melanoma as monotherapy or in combination with ipilimumab, and is also licensed for the treatment of locally advanced or metastatic non-small cell lung cancer after prior chemotherapy, and as monotherapy of advanced renal cell carcinoma. Comprehensive pharmaceutical information for nivolumab is contained in the manufacturer's Summary of Product Characteristics (SmPC). Briefly, nivolumab is a clear to opalescent, colourless to pale yellow solution of pH 6.0 and osmolality of 340 mOsm/kg supplied as a 10 mg/mL sterile concentrate for solution for intravenous infusion. Nivolumab (Opdivo®) will be purchased by the host institution for use in the trial and stored at 2°-8°C in the clinical trials pharmacy until expiry date stated in the SmPC. It will be dispensed for use in ADVANCE from the pharmacy following receipt of a trial-specific prescription and labelled according to the Medicine for Human Use (Clinical Trials) Regulation 2004. All movements of nivolumab between the host institution pharmacy and the clinical sites will be documented.

The recommended dose of nivolumab for current licenced indications is 3 mg/kg administered intravenously every 2 weeks or a flat dose of 480 mg administered intravenously every 4 weeks. The new dose of 480 mg 4-weekly was approved by FDA in March 2018 (https://www.accessdata.fda.gov/drugsatfda_docs/label/2018/125554s048s049s050s051s052s061s062s064s065s066lbl.pdf).

Therefore, this study will make use of a uniform intravenous dose of nivolumab 480mg per infusion, administered on one or three occasions only, at an interval of 4 weeks apart.

Nivolumab (Opdivo®) for this study will be supplied by a commercial company, Vaccitech Ltd., that will have access to the study results.

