In this study ChAdOx1.5T4 and MVA.5T4 vaccines are administered in a single injection at the dose of 2.5×10^{10} vp and 2×10^8 pfu respectively. Low- or intermediate-risk prostate cancer patients will receive one cycle of ChAd and MVA immunisation with the vaccines given one week apart. Metastatic prostate cancer patients will receive two cycles of ChAd-MVA immunisations with the vaccines given four weeks apart. This is intended to boost the elicited immune response and to maintain the pool of antigen-specific memory T cells. The interval between the cycles will be approximately 2 months. In the recently completed phase I trial there was similar immunogenicity with intervals between the ChAd and MVA vector administration of 1 and 4 weeks. The 1 week interval is likely to be preferred by low and intermediate risk patients as this reduces time to surgery.

[figure not shown]
PD-1 mAb (nivolumab, Opdivo®) is administered intravenously at a uniform dose of 480mg per infusion. Low- or intermediate-risk prostate cancer patients will receive one intravenous infusion of nivolumab concomitantly with MVA.5T4 vaccine (i.e. on the same day as the vaccine). Metastatic prostate cancer patients will receive three intravenous infusion of nivolumab four week apart, with the first dose given concomitantly with the first MVA.5T4 vaccine.

The dosing regimens for each arm are shown in the diagram below.

Group 1 dosing regimen

Group 2 dosing regimen

Selection of the study patient cohort

Low- or intermediate-risk localised or locally advanced prostate cancer patients undergoing RP.

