Checkpoint inhibitor treatment is associated with immune-mediated adverse reactions which may affect any organ system. Current data on the incidence of immune-related toxicities are derived from a number of large phase III clinical trials administering weeks to months of continuous checkpoint inhibitor therapy until disease progression, loss of clinical benefit or unacceptable toxicity, in a range of non-prostate tumour types. This study, however, will make use of a **restricted course of treatment limited to 3 infusions 4 weeks apart for metastatic PCa patients and only 1 infusion for low- or intermediate- risk PCa patients**. The incidence and severity of immune-mediated toxicities following a limited course of 3 infusions four weeks apart is not publically available. However, immune-mediated adverse events may occur at any time from the onset of therapy or after completion of treatment and may not be dose-dependent. Most immune-related adverse reactions, however, are low in severity and resolve with appropriate management, though fatal cases have been reported.

The frequency and median time to onset for the major immune mediated toxicities from pooled phase III datasets are shown in Table 1. These data relate to continuous therapy regimes with repeat nivolumab infusions at 2 week intervals. The incidence of toxicities grade 3 or above is <2% for all organ systems. Importantly, more than 50% of immune-mediated toxicities develop after several weeks of continuous treatment, therefore the frequency and risk of treatment-related adverse events following a restricted course of 3 infusions in this study is anticipated to be considerably lower than during licenced clinical use.

Table 1. Immune mediated adverse events after continuous monotherapy with Nivolumab

Immune-mediated toxicity	Frequency (%) *		Median (range) time to onset (months)	Corresponding number of doses at median time of onset **
	Any severity	Grade 3 or above		
Rash	25.6	0.9	1.4 months(0.0-113.7)	3
Diarrhoea / Colitis	12.6	1.3	1.4 months (0.0-20.9)	3
Pneumonitis	3.0	0.8	3.3 months (0.0-19.6)	7
Liver dysfunction/ Hepatitis	6.4	1.8	1.9 months (0.0-10.4)	4
Renal dysfunction	2.7	0.5	2.3 months (0.0-18.2)	5
Endocrinopathy				
Thyroid disorders	8.5	<0.1	2.8 months (0.0-14.0)	6

Adrenal insufficiency	0.4	0.2		
Pituitary disorders	0.4	0.2		

* From pooled dataset n = 2227 (CA209066, CA209037, CA209067 trials) nivolumab 3mg/kg across tumour types

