5.5. Delay and discontinuation criteria

Discontinuation rules

Treatment with study vaccines and checkpoint inhibitors should be permanently discontinued under the following circumstances:

- On withdrawal of informed consent i.e. the subjects request to discontinue
- Any immune-related checkpoint inhibitor toxicity \geq Grade 3 in severity in the following organ systems:
 - o Dermatological
 - o Gastrointestinal, hepatic or hepatobiliary
 - o Respiratory
 - o Renal
 - o Endocrine
 - o Neurological (apart from headache)
 - o Haematological
- Any infusion reaction of \geq Grade 3 severity

- Any significant clinical disorder, laboratory finding or adverse event, in the judgment of the Investigator makes it unsuitable for the participant to continue study treatment.

Dose delay criteria

Treatment with study vaccine and / or checkpoint inhibitor should be delayed under the following circumstances:

- If the subject has a temperature of > 37.5 °C.
- Any immune-related checkpoint inhibitor toxicity of < Grade 3 in severity, until symptoms have resolved and management with corticosteroids (if indicated) is complete
- Any grade 2 electrolyte disturbance (i.e. abnormalities in serum sodium, potassium, calcium or magnesium), until appropriate correction / replacement has been initiated
- Any significant clinical disorder, laboratory finding, adverse event or intercurrent illness which in the judgment of the Investigator makes it unsuitable for the participant to proceed with treatment.

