Assessment & recording of adverse events		X	X	X	X	X	X	X	X	X
Radiological assessment (bone scintigraphy, CT scan, MR scan)		X ¹								
Patient alert card provided		X								
Diary card provided		B			C			D		
Diary card returned				X				X		
Haematology ²	2	2		2	2		2	2		2
Biochemistry ²	4	4		4	4		4	4		4
Serum glucose ²	2	2		2	2		2	2		2
Thyroid function tests ²⁻³	2	2						2		
PSA ¹	5	5		5	5		5	5		5
Urinalysis	X	X		X	X		X	X		X
HBsAg, HIV &HCV Ab ¹	5									
Human leukocyte antigen typing (ml)				5						
Exploratory immunology (ml)		30		40			40			40
CTC (ml)		8						8		
ctDNA (ml)		8			8			8		

Total blood volume per visit (ml) ²	20	61		58	21		53	31		53
--	----	----	--	----	----	--	----	----	--	----

* Window is based on preceding IMP administration

¹ Window is -28 days

² Volume can vary by site according to local practices

³ Total triiodothyronine (T3) or free T3c, free thyroxine (T4) and thyroid stimulating hormone (TSH)

Group 2: Participants with Metastatic Prostate Cancer

Table of events (part 2 of 2)

Visit/Telephone Call Number	V7	T4	V8	V9	T5	V10	V11	V12	V13
Time from enrolment (weeks+days)	12	12[contact][contact]
Window (days)*	±7	+3	+3	±2	+3	+3	±7	±14	±14
Informed consent									
Review of inclusion/exclusion criteria	X		(X)	X		(X)	(X)	(X)	(X)
Medical history	(X)		(X)	(X)		(X)	(X)	(X)	(X)
Physical examination (if required)	(X)		(X)	(X)		(X)	(X)	(X)	(X)
Telephone Call		X			X				
Recording vital signs	X		X	X		X	X	X	X
ECOG Status	X			X			X	X	X
ChAdOx1.5T4 vaccination	X								
MVA.5T4 vaccination				X					
Nivolumab infusion	X								
Assessment & recording of adverse events	X	X	X	X	X	X	X	X	X
Radiological assessment (bone scintigraphy, CT MR scan)							X		X
Diary card provided	C			B					
Diary card returned	X			X		X			
Haematology ¹	2		2	2		2	2	2	2
Biochemistry ¹	4		4	4		4	4	4	4
Serum glucose ¹	2		2	2		2	2	2	2
Thyroid function tests ^{1, 2}	2			2			2	2	2
PSA ¹	5		5	5		5	5	5	5
Urinalysis	X		X	X		X	X	X	X
Exploratory immunology (ml)			40			40	30	40	40
CTC (ml)							8		
ctDNA (ml)	8						8		
Total blood volume per visit (ml) ¹	23		53	15		53	61	55	55

Cumulative blood volume = 612m¹

* Window is based on preceding IMP administration

¹ Volume can vary by site according to local practices

² Total triiodothyronine (T3) or free T3c, free thyroxine (T4) and thyroid stimulating hormone (TSH)

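### The week-12 visit window lets nivolumab 480 mg be repeated after 21 days, although the dose rests on a 4-week interval

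*Protocol*

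**What the plan says.** Section 4.2.2 gives the recommended nivolumab schedules for current indications as "3 mg/kg administered intravenously every 2 weeks or a flat dose of 480 mg administered intravenously every 4 weeks". From the second it derives the trial regimen of 480 mg per infusion, "administered on one or three occasions only, at an interval of 4 weeks apart". Section 2.2 repeats the interval for Group 2 ("Metastatic prostate cancer patients will receive three intravenous infusion of nivolumab four week apart"), and so does the risk discussion in section 4.6.4 ("limited to 3 infusions 4 weeks apart for metastatic PCa patients"). Section 4.3 places the three infusions at weeks 4, 8 and 12.

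Appendix 1 sets the tolerances. In part 2 of the Group 2 table the row reads "Window (days)* ±7 +3 +3 ±2 +3 +3 ±7 ±14 ±14". Its first entry belongs to V7, the week-12 visit with the third nivolumab infusion and the second ChAdOx1.5T4 injection. The footnote states: "Window is based on preceding IMP administration". The other windowed Group 2 dosing visits are V3 (week 4), V5 (week 8) and V9 (week 16), each with ±2 days.

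Section 5.5 lists clinical reasons for postponing a dose ("Treatment with study vaccine and / or checkpoint inhibitor should be delayed under the following circumstances"). It contains no minimum time between infusions, and no other section sets one.

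**The concern.** The 4-week interval is the stated reason for choosing 480 mg, and the risk discussion assumes it. The schedule nevertheless allows the third infusion a full week early. V7 stands out: elsewhere in Appendix 1, ±7 days appears only at visits without study drug (Group 2 V11; Group 1 V4, V5 and V6), and Group 1's own nivolumab visit (V2) allows +3 days with no early side. V7 gives two study drugs on one day under a tolerance otherwise kept for follow-up visits, and no reason is given.

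Two things are at stake. Patients could receive the flat dose at a spacing the dose rationale does not cover. Exposure could also vary more between patients in a trial where safety of the combination is a co-primary objective. Section 4.6.4 itself says that toxicity data for three infusions at 4-week spacing are not publicly available, so closer spacing has even less support in the document.

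The point is limited to the early side of V7. A tolerance around a nominal date is normal, and ±2 days at the other dosing visits is not questioned. The late side of V7 does not shorten any gap, and section 5.5 already permits delay.

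**Working it through.** **Inputs**

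| Input | Value | Source |
|---|---|---|
| Dose per infusion | 480 mg | 4.2.2, 4.3 |
| Number of infusions, Group 2 | 3 (total 1440 mg) | 4.3 |
| Nominal times | weeks 4, 8, 12 | 4.3 |
| Window at V5 (week 8) | ±2 days | Appendix 1, Group 2, part 1 |
| Window at V7 (week 12) | ±7 days | Appendix 1, Group 2, part 2 |
| Anchor of the window | previous study drug | Appendix 1 footnote |

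**The plan's own figure.** Nominal gap from week 8 to week 12: (12 − 8) × 7 = 28 days, which matches the stated 4 weeks.

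**Gaps the windows allow** (nominal gap ± window, counted from the previous study drug)

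- Week 4 to week 8: 28 ± 2 = 26 to 30 days.
- Week 8 to week 12: 28 ± 7 = 21 to 35 days. The study drug before V7 is the week-8 nivolumab.
- Counting from enrolment instead would allow an even shorter gap, with V5 two days late and V7 seven days early: (84 − 7) − (56 + 2) = 19 days. The 21 days follows from the footnote's own rule and is the milder reading.

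**Dose rate over the single gap** (480 mg ÷ days × 7)

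- 28 days: 120 mg/week.
- 26 days: 129 mg/week (+7.7%).
- 21 days: 160 mg/week (+33%).

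**Dose rate over the course** (1440 mg ÷ total days × 7). The total is the two gaps plus 28 days after the third dose. That 28-day tail is a convention chosen here, not taken from the protocol.

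| Scenario | Days | mg/week | Against nominal |
|---|---|---|---|
| Nominal | 28 + 28 + 28 = 84 | 120.0 | – |
| V7 at 21 days | 28 + 21 + 28 = 77 | 130.9 | +9.1% |
| V5 at 26 and V7 at 21 days | 26 + 21 + 28 = 75 | 134.4 | +12.0% |
| V7 at 26 days (proposed limit) | 28 + 26 + 28 = 82 | 122.9 | +2.4% |
| V5 and V7 both at 26 days (proposed limit) | 26 + 26 + 28 = 80 | 126.0 | +5.0% |

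**First to third infusion.** Nominal 28 + 28 = 56 days. Shortest now 26 + 21 = 47 days. Shortest under a 2-day early limit at V7: 26 + 26 = 52 days.

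**The case against.** The strongest reply is that nothing here is contradictory. Sections 2.2, 4.2.2, 4.3 and 4.6.4 state a nominal interval, and Appendix 1 adds a tolerance. If 26 days is acceptable at V5, then 28 days is not a floor, and no text says where the line lies between 26 and 21. It stands that the 26-day limit is borrowed from the protocol's practice at V5 and is not derived from pharmacology.

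Section 4.2.2 also cites 3 mg/kg every 2 weeks, which is 1.5 mg/kg/week. At that rate, 120 mg/week corresponds to a man of 120 ÷ 1.5 = 80 kg and 160 mg/week to one of about 107 kg. A 60 kg man given 480 mg exactly on time already receives 120 ÷ 60 = 2.0 mg/kg/week, 33% above 1.5. (The protocol gives no patient weights; 60 kg is an illustration.) A one-off +9% to +12% is therefore within variation that flat dosing already accepts. This stands and limits the severity, but it does not supply a rationale for a shorter gap with the flat dose.

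Safeguards also apply at V7 on whatever day it falls. Haematology and biochemistry are reviewed before dosing, although thyroid results are excluded from that review. Immune-related toxicity delays or stops treatment under section 5.5. Total dose is fixed, and section 4.6.4 says immune-mediated events may not depend on dose. These are real protections against dosing a patient with detected toxicity, but they do not control the interval.

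Finally, V7 opens the second vaccine cycle, whose spacing section 2.2 gives only as roughly two months. That could justify flexibility for the vaccine. It does not explain giving nivolumab early.

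**Conclusion.** The concern holds. As written, Appendix 1 permits a 21-day gap between the second and third 480 mg infusions, against the 4 weeks from which the dose is derived, and no rule elsewhere prevents it. It affects one interval per Group 2 patient. The worst case is 160 against 120 mg/week over that gap and +9% to +12% over the course. The course figures depend on the 28-day tail and on a site using the full early allowance; how often sites would do so is unknown.

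This is a modest matter of safety and consistent exposure. The protocol does not show that 21 days is harmful, and sample size, power and error rates are unaffected. It should be corrected because the schedule and the dose rationale disagree at little cost to repair.

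**What to change.** In Appendix 1, Group 2, part 2, change the V7 window from ±7 to −2/+7 days. Add to the window footnote: *No nivolumab infusion is given less than 26 days after the previous one.* This uses the early limit already in force at V5 and keeps the late flexibility at V7. V9 is counted from V7 and needs no change.

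The cost is one table cell and one sentence. The permitted V7 dates go from days 21–35 after the week-8 infusion (15 days) to days 26–35 (10 days), so visits on days 21 to 25 would become deviations.
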